#### 5. TREATMENT PLAN

##### 5.1. IRX5183 Administration:

IRX5183 is an oral capsule that will be administered once daily. Reported adverse events and potential risks are described in Section 9. Appropriate dose modifications are described in Section 6. No investigational or commercial agents or therapies other than those described below may be administered with the intent to treat the patient's malignancy. Patients will be instructed to take the daily dose of IRX5183 each morning after food, as close to the same time as possible. IRX5183 will be self-administered at home, except for days 1 and 14 of cycle 1, on which patients will receive their doses in clinic after trough PK levels are drawn. Each patient will keep a pill diary to help with compliance. If a patient forgets to take a dose in the morning and it is before 8:00 p.m., they should be instructed to take their dose. If the subject forgets to take their daily dose and it is after 8:00 p.m., they should be instructed to wait for the next morning to dose. If vomiting occurs after dosing, the subject should not receive another dose, but instead wait until the next morning to dose.

The schedule of IRX5183 administration and the dose escalation schema are shown in figure 2 and table 1, respectively. At any point, patients will be withdrawn from treatment for undue toxicity, disease progression, and/or deterioration of performance status, per guidelines in section 3.5 above. For **induction therapy**, single agent IRX5183 will be administered orally once daily for two 28-day cycles. Bone marrow assessments will be performed after each cycle, but the primary assessment/endpoint is after cycle 2 of induction. IRX5183 may be held for 5-7 days post induction therapy to allow for study drug wash-out if the PI has concerns that the drug is limiting the interpretation of the assessment marrow testing needed to measure response. All study patients who have drug held only for marrow assessment are eligible to resume study drug following the completion of the marrow testing, while awaiting final pathology review and response assessment.

Patients achieving at least SD, i.e. CR, partial remission (PR), hematologic improvement (HI), or SD,

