## 7.8. Pharmacokinetics:

In phase I, we plan to first determine pharmacokinetic (PK) parameters of IRX5183 on days 1 and 14 ( $\pm$ 3) of cycle 1 in the PB and BM compartments (may be obtained post cycle 1 if day 14 BM specimen not available). In phase II, we will perform confirmatory testing at these time points in a subgroup of patients. Full sampling, processing, storage, and shipment instructions will be provided in the Laboratory manual. Briefly, trough and peak levels of IRX5183 will be determined in the plasma and mononuclear cells (MNC) by obtaining a 4 mL sample of blood (green top tubes-sodium heparin)  $\frac{1}{2}$  hour before the morning dose and then 2 hours ( $\pm$  30 minutes) post drug administration. Phase I PK data showed that  $T_{max}$  generally was in the range of 1-3 hours post dose across individual patients. We will isolate platelet rich plasma (PRP) and

MNC and samples will be frozen in our laboratory, and then shipped and analyzed in a batch on dry ice to the laboratory of [name] at the University of Maryland. Drug levels will be determined by liquid chromatography mass spectroscopy (LCMS), per techniques as previously reported (Kane, 2012).

Peak drug levels will also be determined in the BM compartment on day 14 ( $\pm$  3 days) (may be obtained post cycle 1 if day 14 BM specimen not available), approximately 1 to 3 hours after dosing (as close to 2 hours post as possible, but up to 4 hours post drug administration). We will allow for flexibility in timing of the BM due to difficulties with scheduling and wait times, but we will aim for collection as close to that of the PB as possible, for optimal comparison of drug concentrations. We are interested to see whether intracellular levels will differ between LSCs, normal hematopoietic stem cells (HSCs), and bulk AML cells, and how these levels compare to plasma. We will isolate BM plasma and MNC from the BM aspirate and sort for LSCs, normal HSCs, and bulk AML (when possible) and then freeze at -80 degrees Celsius (as per the Lab Manual and section 8.2 below). Depending on the type of AML, we may not be able to isolate CD34+CD38ALDHint LSCs, in which case we will isolate CD34+CD38 cells. Samples will be shipped and analyzed in a batch at the end of the study by LCMS in the laboratory of [name], as above.

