## 8. CORRELATIVE STUDIES

### 8.1. Biologic activity:

Assessing the biologic activity of IRX5183 in AML and MDS patients is critical to the interpretation of any clinical activity. Successful induction of terminal differentiation would be expected to be measurable by changes in the malignant cell phenotype as well as possible cytogenetic changes. The following biologic correlatives will be conducted in the laboratories of Drs. [name] and [name]:

1. ***In vivo* induction of terminal differentiation** - PB and BM markers of myeloid differentiation such as CD15 and CD11b (as directed by disease phenotype) will be measured by flow cytometry prior to the initiation of therapy and repeated on the day 14 ( $\pm$  3) and/or post cycle 1 specimens, with a preference for day 14 ( $\pm$  3), while ongoing differentiation is more likely.
2. **Effect on leukemia stem cells as an indicator of differentiation** – ratio of LSC population to normal HSC population will be determined at baseline, day 14 ( $\pm$  3 days), and later endpoints in select patients. If the patient's leukemia consists of an ALDH intermediate population, we will determine the ratio of CD34+CD38ALDHint LSCs to

CD34+CD38ALDHhigh normal HSCs. We will use techniques as we have previously published (Gerber et al., 2012).

3. ***In vivo* changes in measurable cytogenetic alterations** – baseline clinical fluorescent in situ hybridization (FISH) analysis will be done prior to starting treatment and subsequent analyses will take place with each clinical BM, in order to assess for a cytogenetic response to therapy. When possible, FISH will additionally be used to quantify the cytogenetic changes in PB and marrow myeloid progenitors prior and following therapy on day 14 ( $\pm$  3 days) and/or after cycle 1. The presence of mature neutrophils with the malignant cytogenetic abnormality in the PB will serve as evidence for terminal differentiation of leukemia cells from the therapy.

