**11.7. Analysis of secondary endpoints:****Pharmacokinetics:**

In the dose escalation phase, we plan to first determine PK parameters of IRX5183 at baseline and day 14 ( $\pm 3$  days) in the PB and BM compartments. In the dose expansion phase, we will perform confirmatory testing in a subgroup of patients at the same time points. PK analyses will be largely descriptive, using Student's t-tests or Wilcoxon rank sum tests comparing drug concentrations at both time points. We will also assess the peak and trough levels in the PB at the above time points.

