**Pharmacodynamics:**

Biologic correlates include measurement of markers of myeloid differentiation by flow cytometry (e.g. CD15, CD11b), BM blast count, and ANC at the different dose levels in the dose escalation phase and at the RP2D in the expansion phase at the different time points compared to baseline. In addition, we will look at the ratio of ANC to BM blast count as clinical marker for differentiation at the different time points compared to baseline. Statistics will be descriptive and will consist of paired Student's t-tests or Wilcoxon rank sum tests comparing averages between 2 time points (e.g. after induction therapy compared to baseline).

We will furthermore assess *in vivo* changes in detectable chromosomal abnormalities in patients with baseline cytogenetic alterations that define their malignant clones. This will be measured by fluorescent in situ hybridization (FISH) with cells from the individual cellular compartments quantified as a ratio of malignant to non-malignant cells (i.e., mononuclear cells with the cytogenetic finding to those without). Successful differentiation would be expected to result in a decrease in mononuclear cells harboring the cytogenetic abnormality. These results will be summarized using descriptive statistics and exploratory plots will be used to illustrate results.

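### Section 11.7 names the Wilcoxon rank sum test, a test for independent groups, for within-patient comparisons over time, and does not say that the PK t-test is paired

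*Combined protocol and SAP*

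**What the plan says.** Section 11.7, Pharmacodynamics, compares differentiation markers, marrow blast count and ANC, including "at the RP2D in the expansion phase at the different time points compared to baseline". The tests named are "paired Student's t-tests or Wilcoxon rank sum tests comparing averages between 2 time points", with the end of induction against baseline given as an example.

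Section 11.7, Pharmacokinetics, describes the analysis as mainly descriptive, "using Student's t-tests or Wilcoxon rank sum tests comparing drug concentrations at both time points". The word paired does not appear in that paragraph.

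The sampling sections show that one set of patients is measured repeatedly:

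- Section 8.1: the markers "will be measured by flow cytometry prior to the initiation of therapy and repeated on the day 14", or after cycle 1.
- Section 7.8 and the Section 10 calendar footnotes: blood drug levels are taken before and 2 hours after the dose on days 1 and 14 of cycle 1. For the expansion, "In phase II, we will perform confirmatory testing at these time points in a subgroup of patients".
- Section 5.1: home dosing applies "except for days 1 and 14 of cycle 1, on which patients will receive their doses in clinic after trough PK levels are drawn".

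**The concern.** The rank sum test treats the two sets of values as coming from different people. Here each later value has a partner from the same patient, and the two are likely to be correlated. A test that ignores this uses the wrong variance for the change. With positive correlation its p-values are too large and real changes are missed. With negative correlation they are too small.

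The PD sentence pairs the parametric test and then offers an unpaired alternative. The PK sentence leaves open whether either test is paired. An analyst who follows the text literally could therefore run an independent-groups analysis on paired data. PK and PD together form secondary objective 1 (Section 1.2), so the results will be read even though no decision rule depends on them.

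**Working it through.** **No plan figure to reproduce.** The documents state no SD, within-patient correlation, effect size or power for these comparisons. The inputs taken from them are the sample sizes in Section 11.4 (27 patients at the RP2D, up to 18 in phase I) and the dose cohorts of 3 to 6 in Section 5.1. Correlation, shift and normality below are assumptions.

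**Step 1: why the level moves.** Take n pairs with common SD σ and correlation ρ. The true variance of the mean change is 2σ²(1 − ρ)/n. An unpaired analysis uses 2σ²/n. The unpaired z statistic therefore has SD √(1 − ρ) under no change, and a nominal two-sided 5% test has a large-sample level of about 2Φ(−1.96/√(1 − ρ)):

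- ρ = −0.3: 1.96/1.140 = 1.719, level 0.086
- ρ = 0: level 0.050
- ρ = 0.3: 1.96/0.837 = 2.343, level 0.019
- ρ = 0.5: 1.96/0.707 = 2.772, level 0.006
- ρ = 0.7: 1.96/0.548 = 3.578, level 0.0004

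This holds for the unpaired t-test and approximately for the rank sum test.

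**Step 2: simulation at n = 27.** Bivariate normal pairs, unit SD, two-sided 0.05, 20,000 replicates per setting. The rank sum p-value is asymptotic and the signed-rank p-value exact.

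| ρ | Level, rank sum | Level, signed-rank | Power at 0.5 SD, rank sum | Power at 0.5 SD, signed-rank |
|---|---|---|---|---|
| −0.3 | 0.083 | 0.052 | 0.42 | 0.33 |
| 0 | 0.048 | 0.049 | 0.41 | 0.41 |
| 0.3 | 0.020 | 0.050 | 0.40 | 0.54 |
| 0.5 | 0.007 | 0.048 | 0.39 | 0.68 |
| 0.7 | 0.001 | 0.050 | 0.37 | 0.88 |

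The simulated levels agree with Step 1. At ρ = −0.3 the rank sum test's higher power only reflects its inflated level. For a 1 SD shift at ρ = 0.5 the gap nearly closes: 0.98 against 1.00.

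**Step 3: the unstated pairing of the PK t-test.** At n = 18 (maximum phase I accrual, all dose levels pooled) and a 0.5 SD shift, power unpaired against paired is 0.28 vs 0.39 at ρ = 0.3, 0.25 vs 0.52 at 0.5, and 0.20 vs 0.73 at 0.7.

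**Step 4: single dose cohorts.** At n = 6, ρ = 0.5 and a 0.5 SD shift, power is 0.06 for rank sum and 0.11 for signed-rank, so little is gained. The smallest exact two-sided signed-rank p-value is 2/2ⁿ: 0.25, 0.125, 0.0625 and 0.031 for n = 3, 4, 5 and 6. With 3 to 5 pairs the test cannot reach 0.05.

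**The case against.** The strongest reply is that this is a naming slip with no consequence. In the PD sentence, the word paired can be read as covering both tests, which would show that the authors knew the structure of the data. A valid paired t-test is already there. Both paragraphs call the analyses descriptive, and neither sets an alpha, a hypothesis or a go/no-go rule.

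Some of this stands. The PD problem is live only if the non-parametric option is chosen and run as an unpaired test. But the rank sum test has no paired form, so the name is wrong on either reading, and the PK paragraph offers no such reading.

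The size can also be challenged, and these limits stand:

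- **Sample size.** 27 is an upper bound for PD: the day 14 marrow is not mandatory (Section 7.2), though Section 8.1 accepts the post-cycle-1 sample. Phase II PK covers only a subgroup.
- **Distribution.** Normal data are where the named t-test already serves. With lognormal data (log-SD 1, shift 0.5 log-SD, ρ = 0.5, n = 27), signed-rank on the raw scale has power 0.61 against 0.38 for rank sum. The gap narrows but remains.
- **Direction.** Nothing in the documents suggests negative correlation, so the likelier harm is lost power rather than false signals.
- **PK scope.** The detailed schedule takes marrow drug levels at day 14 (or after cycle 1) only, so the PK point applies in practice to peripheral blood.

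A rank sum test would suit comparisons between dose levels, but both sentences compare time points.

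**Conclusion.** The concern holds and is minor. Both paragraphs name an independent-groups test for paired data, and the PK paragraph does not say that its t-test is paired. Under the assumed positive correlations of 0.3 to 0.7 with 27 pairs, a nominal 5% rank sum test has an actual level of 2.0% down to 0.1%. Against signed-rank it loses about 0.14 to 0.51 in power for a 0.5 SD shift (0.54 − 0.40 and 0.88 − 0.37). The loss is small in a cohort of 6 and nearly absent for a 1 SD shift at correlation 0.5. These sizes depend on the assumed correlation, shift and normality; that the wrong test is named does not. The RP2D, the Simon design and the primary analysis are unaffected.

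**What to change.** In both paragraphs of Section 11.7, specify paired t-tests or Wilcoxon signed-rank tests for comparisons between time points, using patients who have both measurements. Keep the rank sum test for independent groups only, such as different dose levels.

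Add one sentence: report the within-patient difference or ratio with a 95% confidence interval, and in dose cohorts of 3 to 6 make this the main output instead of a p-value. This sentence is a reporting improvement that goes beyond correcting the error.

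One caution for PK: if day 1 and day 14 concentrations are tested against each other, use the 2-hour post-dose level, because the day 1 trough is drawn before any study drug has been taken.

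Cost: two test names, one added word and one sentence. No extra patients, samples or visits.

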### **11.3. Secondary endpoints:**

1) Phase I - Description of PK parameters of IRX5183 at baseline and day 14, both in the peripheral blood and BM compartments, markers of myeloid differentiation by flow cytometry (e.g. CD15, CD11b), BM blast count, ANC before and after treatment, and changes in detectable cytogenetic abnormalities in the blood and BM compartments at the different dose levels. We will also describe best response per IWG criteria at any time, time to first and best response, and clinical parameters such as transfusion requirements, blood counts, quality of life assessments, and time to either progression or death.

2) Phase II – Description of IWG response and other clinical criteria assessed in the dose escalation phase for the RP2D. We will also measure markers of differentiation assessed in the dose escalation phase for the RP2D, and lastly, the toxicity profile at the RP2D dose.

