**APPENDIX A2. Modified International Working Group (IWG)-2006 response criteria for altering natural history of MDS.**

Category	Response criteria (responses must last at least 4 wk)
Complete remission	
Bone marrow: <math>\leq 5\%</math> myeloblasts with normal maturation of all cell lines*
 
Persistent dysplasia will be noted**†
 
Peripheral blood‡
 
Hgb <math>\geq 11</math> g/dL
 
Platelets <math>\geq 100 \times 10^9/L</math>
 
Neutrophils <math>\geq 1.0 \times 10^9/L</math>†
 
Blasts 0%

Partial Remission	
All CR criteria if abnormal before treatment except:
 
Bone marrow blasts decreased by <math>\geq 50\%</math> over pretreatment but still <math>> 5\%</math>
 
Cellularity and morphology not relevant

Marrow CR†	
Bone marrow: <math>\leq 5\%</math> myeloblasts and decrease by <math>\geq 50\%</math> over pretreatment†
 
Peripheral blood: if HI responses, they will be noted in addition to marrow CR†

Stable disease	Failure to achieve at least PR, but no evidence of progression for $> 8$ wks
Failure	Death during treatment or disease progression characterized by worsening of cytopenias, increase in percentage of bone marrow blasts, or progression to a more advanced MDS FAB subtype than pretreatment
Relapse after CR or PR	
At least 1 of the following:
 
Return to pretreatment bone marrow blast percentage
 
Decrement of <math>\geq 50\%</math> from maximum remission/response levels in <math>\square</math>granulocytes or platelets
 
Reduction in Hgb concentration by <math>\geq 1.5</math> g/dL or transfusion dependence

Cytogenetic response	
Complete
 
Disappearance of the chromosomal abnormality without appearance of new ones
 
Partial
 
At least 50% reduction of the chromosomal abnormality
 
For patients with:

Disease progression	
Less than 5% blasts: <math>\geq 50\%</math> increase in blasts to <math>> 5\%</math> blasts
 
5%-10% blasts: <math>\geq 50\%</math> increase to <math>> 10\%</math> blasts
 
10%-20% blasts: <math>\geq 50\%</math> increase to <math>> 20\%</math> blasts
 
20%-30% blasts: <math>\geq 50\%</math> increase to <math>> 30\%</math> blasts
 
Any of the following:
 
At least 50% decrement from maximum remission/response in granulocytes or platelets
 
Reduction in Hgb by <math>\geq 2</math> g/dL
 
Transfusion dependency <math>\square</math>

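### The FISH measure in section 11.7 is an abnormal-to-normal cell ratio, which has no value at 100% abnormal and is unstable in both directions near it; the proportion of abnormal cells would serve better (low severity).

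*Combined protocol and SAP*

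**What the plan says.** Section 11.3 lists among the phase I secondary endpoints "changes in detectable cytogenetic abnormalities in the blood and BM compartments at the different dose levels". Section 11.7 (Pharmacodynamics) restricts the analysis to patients "in patients with baseline cytogenetic alterations that define their malignant clones" and describes the assay: "This will be measured by fluorescent in situ hybridization (FISH) with cells from the individual cellular compartments", with the result "quantified as a ratio of malignant to non-malignant cells (i.e., mononuclear cells with the cytogenetic finding to those without".

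The expected drug effect is given as a direction: "Successful differentiation would be expected to result in a decrease in mononuclear cells harboring the cytogenetic abnormality". On analysis, the plan says only: "These results will be summarized using descriptive statistics and exploratory plots will be used to illustrate results". It states no number of cells to be scored, no rule for a zero denominator, no log or percentage scale, and no cut-off on the ratio.

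Two other places bear on the point. Section 8.1 plans FISH with each clinical marrow to look for a cytogenetic response, and adds a readout that does not use the ratio: "The presence of mature neutrophils with the malignant cytogenetic abnormality in the PB will serve as evidence for terminal differentiation of leukemia cells". Appendix A2, the MDS criteria, defines a partial cytogenetic response as "At least 50% reduction of the chromosomal abnormality" without naming the scale.

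**The concern.** If k of n scored cells are abnormal, the plan's measure is k/(n−k). It behaves well when a reasonable number of normal cells is present and badly when few are. The endpoint is confined to patients with a clone-defining abnormality, in relapsed or refractory AML and high-risk MDS, and is measured in separate cell compartments. Very high abnormal fractions are plausible there, although the documents give no distribution.

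What is at stake is how the result reads. Phase I describes cytogenetic change by dose level, and Table 2 in section 5.2 gives cohorts of 3 to 6 patients, fewer once those without an abnormality are set aside. In a group that small, one patient near 100% can set the summary, and a change of one or two cells in that patient can look like a large shift. A patient with no normal cells scored has no value at all, and the plan does not say whether that patient is dropped, capped or reported separately.

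**Working it through.** The plan gives no precision or sample-size figure for this measure, so there is none to reproduce.

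**Inputs**
- Measure: r = k/(n−k), from section 11.7.
- Cells scored per sample, n: not stated. Assumed 200, with 100 and 500 as a range.
- True abnormal fraction, p: not stated. Values from 60% to 99% are shown.
- No true change: baseline and follow-up counts are independent Binomial(n, p) with the same p. This covers counting noise only, not assay cut-offs or differences between marrow samples.

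**Undefined values.** The chance that one sample has no normal cell is pⁿ. The chance that at least one of two samples is undefined is 1 − (1 − pⁿ)². With n = 200:
- p = 0.98: pⁿ = 1.8%, and 3.5% for the pair.
- p = 0.99: pⁿ = 13.4%, and 25% for the pair.

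**Instability.** One extra normal cell takes 199/1 = 199 to 198/2 = 99, although 99% of cells are still abnormal. The table gives, by exact enumeration, the chance that both ratios are defined and the follow-up is at most half the baseline. The chance that it at least doubles is identical, because the two counts are interchangeable when nothing has changed.

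| True % abnormal | n = 100 | n = 200 | n = 500 |
|---|---|---|---|
| 60 | 0.9% | 0.04% | <0.01% |
| 80 | 2.7% | 0.3% | <0.01% |
| 90 | 7.9% | 2.3% | 0.08% |
| 95 | 17.2% | 7.9% | 1.1% |
| 98 | 20.3% | 20.1% | 8.2% |
| 99 | 10.1% | 20.3% | 17.7% |

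The 10.1% at 99% with 100 cells is low only because 60% of pairs are undefined there. Among pairs with both ratios defined, the n = 200 figures are 20.8% at 98% and 27.0% at 99%.

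On the proportion scale k/n, a fall by half has a probability below one in ten million in every cell of this table.

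**Effect on a small group.** Take three hypothetical patients at 50%, 70% and 99% abnormal.
- Ratios: 0.50/0.50 = 1.00, 0.70/0.30 = 2.33, 0.99/0.01 = 99.0. Mean = 102.33/3 = 34.1.
- The last patient moves to 98%: 0.98/0.02 = 49.0. Mean = 52.33/3 = 17.4.
- Mean share: (50 + 70 + 99)/3 = 73.0%, then (50 + 70 + 98)/3 = 72.7%.

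**Scale of a 50% rule.** At 98% the ratio is 49. Half is 24.5, which corresponds to 24.5/25.5 = 96.1% abnormal. On the proportion scale that is a relative fall of (98 − 96.1)/98 = 1.9%.

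**The case against.** A reader might infer from these figures that an inert drug could appear to clear the clone. The documents and the arithmetic do not support that. Clearance means a ratio near zero. When noise alone halves the ratio with 200 cells, the follow-up sample still averages 97.2% abnormal cells at a true 98%, and 98.4% at a true 99%. Rises are as frequent as falls, so the noise carries no lean towards benefit.

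A reader might also infer that noise would produce false partial cytogenetic responses. That would require the 50% rule in Appendix A2 to be applied to the ratio, and nothing in the protocol does so. That rule also belongs to the MDS criteria. Section 7.2 categorises AML patients by Appendix A1, where cytogenetic CR requires normal cytogenetics. What stands is narrower: the documents do not say which scale the 50% refers to, and section 11.7 quantifies FISH only as the ratio.

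Three further points limit the concern, and all stand.
- The plan names no mean of raw ratios. Medians and per-patient plots fit its wording equally well, so the three-patient example shows a risk, not a planned analysis.
- Both the cell count and the abnormal fractions are assumptions. If few patients are above about 90%, little is affected.
- The endpoint plays no part in the DLT assessment, the choice of RP2D, the two-stage rule or the response rate, and the neutrophil readout in section 8.1 is separate evidence of differentiation. Where the ratio is defined, it converts exactly to a proportion, r/(1 + r).

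None of this supplies a value at 100% or steadies the measure near it.

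**Conclusion.** The point holds as a low-severity matter, for consideration. The stated ratio has no value when all scored cells are abnormal, the plan has no rule for that case, and near 100% the ratio is too unstable, up and down, for single-patient or small-cohort changes to be read safely. With 200 cells and no true change, it halves in about 8% of patients at 95% abnormal and about 20% at 98% to 99%, and doubles as often. At 90% or below the figure is at most 2.3%; with 100 cells it would be 7.9% at 90%. These sizes rest on an assumed cell count, assumed abnormal fractions and pure counting noise. No trial decision depends on the measure, so the consequence is confined to how a descriptive secondary endpoint is reported and understood.

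**What to change.** In section 11.7, replace the ratio with the proportion of abnormal cells among all cells scored, k/n, for each cell compartment. Report the number of cells scored, an exact binomial interval for each proportion, and the within-patient change from baseline in percentage points. This is defined at 100% and matches the direction of effect the section already describes.

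Add one clause: where the Appendix A2 cytogenetic response rule is used, for MDS patients, the 50% reduction is taken on this proportion, while AML patients stay under Appendix A1.

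The cost is a sentence or two of text. The samples, cell counts and assay are unchanged.
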